#### 4.2 SCIENTIFIC RATIONALE FOR STUDY DESIGN

We are using a parallel randomized controlled design with 12 month follow-up to determine the efficacy and short-term durability of the effects of Noom on weight and associated changes in psychosocial and health. We chose an active control condition (Noom Digital Health) to control for proactive engagement in health related dietary and physical activity changes. These efforts are driven by expert information and

our control condition provides this expert information, consistent with CDC guidelines for healthy lifestyle. It is designed to reflect readily available expert information on weight loss and management in the community and adapted into a digital format to control for delivery method.

#### 4.3 JUSTIFICATION FOR INTERVENTION

Commercial and medical weight loss interventions typically vary from 3-6 months with maximal weight loss achieved for the majority of participants within the first 3-4 months and rarely reaching maximal weight loss after 6 months of active intervention. Maintenance is an active process and requires a different set of skills and practices, so the Noom intervention builds on these behavioral weight loss and lifestyle intervention data to utilize expert coaching to increase uptake and contextualization of these skills in the individual's natural environment through coaching led smartphone assisted behavioral interventions targeting diet, exercise, and lifestyle. Observational data support 5-10% weight loss from the Noom app with adherence moderating this effect to a moderate degree. Consequently, Noom offers a digital adaptation of existing and well established behavioral weight loss interventions and maximized the windows of time for weight loss and maintenance based on these data.

#### 4.4 END-OF-STUDY DEFINITION

A participant is considered to have completed the study if he or she has completed the baseline assessment, 6 months intervention, 6 months active maintenance and the 1-month, 4-month, 6-month, 12-month, 18-month, 24-month, and 30-month follow-up assessments.

The end of the study is defined as completion of the 30-month follow-up assessment shown in the Schedule of Activities (SoA), **Section 1.3**.

### 5 STUDY POPULATION

#### 5.1 INCLUSION CRITERIA

- Interested in the Noom platform
- BMI  $> 27 \text{ kg/m}^2$
- Between the ages of 18 and 60 at entry to the study
- Speak English

#### 5.2 EXCLUSION CRITERIA

- Contraindication to smartphone use (e.g., seizures from prior smartphone use, do not own a smartphone).

- Acute suicide risk
- Pregnancy
- Current and planned breastfeeding\*

Individuals who are pregnant should not participate in a medically unsupervised weight loss program due to the risks associated.

\* Added after recruitment closed

### 5.3 LIFESTYLE CONSIDERATIONS

During this study, participants may be asked to make significant changes to their lifestyle in relation to food intake and physical activity as recommended by the Noom coaches.

### 5.4 SCREEN FAILURES

Formal withdrawal, removal of the Noom app, or failure to complete scheduled measures will constitute drop-out for the study.

### 5.5 STRATEGIES FOR RECRUITMENT AND RETENTION

Participants will be recruited from Noom and from the Center for Excellence for Eating and Weight Disorders Program (EWDP) at the Icahn School of Medicine at Mount Sinai

*Noom.* Participants will have signed up with Noom directly to hear about research studies or have viewed the ad on the Noom app. These ads will contain a recruitment link to direct the participants to the research team.

*EWDP.* Patients or providers calling the Center for Excellence for Eating and Weight Disorders Program (EWDP) at the Icahn School of Medicine at Mount Sinai requesting information about research options for weight loss treatment will be emailed the recruitment link. A description will be provided as well.

*Link.* Upon clicking the recruitment link, participants will be directed to a 5-minute REDCap survey. The first page of the survey will include a description of the study. The second page will include [3 questions which will help with the booking process of the Zoom consent.](#)

*PPHS Guidance.* This recruitment process aligns with the PPHS guidance > Screening Guidelines > Section 1, page 1, indicating that basic screening can take place prior to informed consent if it's part of the recruitment process. By incorporating this initial eligibility survey before the informed consent, we reduce burden for participants who are not eligible by lessening

the contacts with them to book a Zoom call, and by not conducting the 30-45 minute Zoom call. Additionally, we minimize risk to them by not collecting any identifiers other than email. By following PPHS guidance > Screening Guidelines > Section III, page 1, we adhere to consent process by having two different consent forms, one for screening and one for the full research study. This process will allow us to follow the HIPAA guidelines indicating that we should only collect as minimal information as possible.

Compensation will be \$35 for the first assessment and \$20 for each additional assessment. Additionally, in an effort to maintain retention, a lottery drawing will take place every 3 months for \$50. Participants who win the lottery and also provided weight at their last follow-up will receive \$100. For participants who are willing provide a social security number, they will be paid in the form of a check, otherwise it will be in the form of an Amazon gift card. The drawing will be done by the project manager in the EWDP office and the winner of the drawing will be notified by email. The winner will be chosen using random number generator

<https://g.co/kgs/J8o9Hy>. The ID numbers of all participants still enrolled will be listed in an excel spreadsheet. In the number generator, a min and max number is entered. For this drawing, the min number entered will be “1” and the max will be the total number (count) of participants who are still enrolled. The number that appears will represent the row in the excel file and will determine the selected winner of that drawing. A purchase is not required for participants to be placed in the drawing. We are using a lottery to incentivize weight because it poses additional time and practical constraints for participants to complete. Because this commitment can vary randomly depending on where in weight loss journey, environmental changes (scale no longer at home, uses gym scale), or timing (assessment scheduled for mid-day when scale not accessible), the lottery offers incentive for those unpredictable extra time-burdens that our participants have reported in the first year of the study.

## 6 STUDY INTERVENTION(S) OR EXPERIMENTAL MANIPULATION(S)

### 6.1 STUDY INTERVENTION(S) OR EXPERIMENTAL MANIPULATION(S) ADMINISTRATION

#### 6.1.1 STUDY INTERVENTION OR EXPERIMENTAL MANIPULATION DESCRIPTION

As approved in the prior Ideate protocol, participants will be randomized to one of the groups for 6 months intervention and 6 months maintenance: (1) Noom app with coaching, administered in a group format (Noom Health; n=300), or (2) Noom Digital Health (n=300).

#### 6.1.2 ADMINISTRATION AND/OR DOSING

All participants will use their assigned app for 6 months of intervention and 6 months of maintenance (12 months total). Subjects will use the app multiple times per day to log eating episodes (the number of

episodes will vary by person). Participants will be encouraged to use the app for 6 months after intervention to maintain weight loss, with goal to maintain weight.

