## 7 STUDY INTERVENTION/EXPERIMENTAL MANIPULATION DISCONTINUATION AND PARTICIPANT DISCONTINUATION/WITHDRAWAL

### 7.1 DISCONTINUATION OF STUDY INTERVENTION/EXPERIMENTAL MANIPULATION

All participants will be contacted to complete all follow-up assessments unless they indicate that they would like to be withdrawn from the study. Participants are instructed in the consent form to contact the research staff directly if they would like to withdraw. Participants may indicate that they would like to withdraw from the intervention, but are still willing to complete future follow-up assessments. Contacts made to these participants will be assessment-related and not intervention-related. Depending on when the participant withdraws and under which circumstances would dictate the remaining procedures that they complete. Research staff will attempt to collect the reason for discontinuing at the time of withdrawal.

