### 9.2 SAMPLE SIZE DETERMINATION

Mt. Sinai will use piecewise latent growth curve models with treatment as primary indicator. Using Monte Carlo simulation studies with 10,000 draws and 6 time points and 2 growth processes, Mt. Sinai evaluated sample size needed to detect significant differences on each growth process (within treatment, post-treatment follow-up). Mt. Sinai also varied missing at random patterns of missing of data at 10%, 20% and 30% increasing linearly over each timepoint. The results indicate that with 30% missing data, mean difference in BMI change of 1.2 (SD =4.5), Mt. Sinai is 85% powered to detect significant difference at 24 month follow-up with N = 600. The power increases substantially for within treatment BMI change .8 (SD =4.5), power = .942. For psychosocial outcomes, N=600 with same parameters indicated 82-90% power to find treatment effects at 24 months, assuming a .20 SD unit difference between groups. Within treatment, the same difference is powered 90-98%.

For Aim 2, Mt. Sinai assumed full information on all moderators and tested the interaction effect with a composite moderator profile of 12 indicators. The interaction between latent moderator (M) and treatment was powered at .93 and .85 with N=600, and 30% attrition for within treatment and follow-up.

For Aim 3 power analyses were based on a 13-item adherence measure adapted from the Noom Monitor (Binge Eating) study and assumes network efficiency of .75. Mt. Sinai would examine the relationship between network entropy and the outcomes, with statistical power for the regression prediction at 100% for each outcome. Mediation model of weekly regular eating is a time series mediation model and assumes latent measure of meal-snack adherence will mediate changes in weight. The calculation is based on effect size goal of .25, .5, and .75. The results of simulations suggest that power for the smallest effect size (.25) is approximately .80 with 10% missing data or less and moderate correlations between time and change in regular eating (.3) and moderate correlation between regular eating and weight outcome (.3).

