- b. Attrition: Formal withdrawal, removal of the Noom app, or failure to complete scheduled measures will constitute drop-out for the study.
- c. Compatibility: We will capture and categorize the type of problems encountered by in the course of the trial and their 'fixes' for individual's phones. Percentage of successful fixes will be our compatibility measure.
- d. Anthropometric Data: Participants will complete a measure of height and weight. As this information will be collected remotely, participants will be asked to use a secure Zoom meeting to complete the weight with a member of the research team viewing the scale.

Smartphone application data from each participant phone will be sent to the centralized secure database at Noom, Inc. that will solely contain data for study participants. The Noom application is HIPAA compliant, and all users will be provided with HIPAA Notice of Privacy Practices. The data will only be identified by a 128-Bit number randomly generated for each participant and data will only be code-based. One electronic copy linking participant names and individualized identifier codes will be stored in a password-protected document on a computer at Noom, Inc. The server system where the data is stored requires an authorization token to log into the system, and a second authorization token to access the database. [name], the Noom, Inc. CTO, is the only person who has access to both tokens.

The proposed study data will be used only for research purposes. Only trained and qualified research team members will have access to study data. To further reduce possible risk to participants, all paper data will be stored in locked rooms and electronic data on password-protected systems. Participants will be assigned a study code, which is the only identifier that will be used when labeling study data. In addition to promoting participant confidentiality, the above measures will also facilitate data sharing with other investigators in the future.

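### Removing the app counts as study drop-out with no time limit, although the app is assigned for only 12 of 30 months and sections 4.4, 7.1 and 7.3 keep such participants in follow-up

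*Combined protocol and SAP*

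**What the plan says.** **Assigned period.** For both arms, section 6.1.2 states "All participants will use their assigned app for 6 months of intervention and 6 months of maintenance (12 months total". On the second half it adds: "Participants will be encouraged to use the app for 6 months after intervention to maintain weight loss, with goal to maintain weight". The schedule in 1.3 marks the intervention at five visits, which fits Day 1 to Day 365. No section says what happens to app access after month 12. The only stated cut-off is in 7.2, for pregnant or breastfeeding participants.

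**Length of study.** Section 4.4: "The end of the study is defined as completion of the 30-month follow-up assessment". The same section defines a completer as someone who has done the baseline assessment, both six-month app periods and all seven follow-up assessments.

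**Drop-out.** Section 10.1.9.1, under Attrition: "Formal withdrawal, removal of the Noom app, or failure to complete scheduled measures will constitute drop-out for the study". Section 5.4, although headed Screen Failures, carries the same sentence. Neither gives a time limit.

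**Leaving the intervention.** Section 7.1: "Participants may indicate that they would like to withdraw from the intervention, but are still willing to complete future follow-up assessments". It has everyone contacted for every follow-up unless they withdraw from the study. Section 7.3 defines loss to follow-up by withdrawal or uncompleted assessments and does not list app removal.

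**Analysis.** Section 9.3 analyses all randomized participants, and 9.1 places the primary hypotheses at 6 and 12 months. Section 9.2 evaluates the "sample size needed to detect significant differences on each growth process (within treatment, post-treatment follow-up" and states 85% power for BMI at 24 months. Section 3 lists, as exploratory, a network model of adherence that should predict study dropout.

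**The concern.** The drop-out rule treats two different things as one: stopping the intervention and leaving the study. During the assigned 12 months that is already at odds with 7.1. After month 12 it has no clear basis, because the participant has finished what was assigned.

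Two outputs are exposed. Attrition reported under 10.1.9.1 would include people whose weights are all observed, so retention would look worse than it is. The exploratory dropout outcome would contain an event, removing the app, that is itself an end to adherence.

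A smaller, related gap is that the plan treats later visits as post-treatment but neither says whether the app remains available nor gives later use a stated place in the analysis. An 18- to 30-month difference could therefore be read as benefit that persists off the app, which the planned data would not show by themselves.

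**Working it through.** **1. The plan's figure for this period.** Section 9.2 gives 85% power at 24 months for a BMI difference of 1.2 (SD 4.5), N = 600, 30% missing. A single-timepoint approximation uses SE = 4.5 × √(2/n) and power = Φ(1.2/SE − z). Alpha 0.05 is my assumption, as none is stated.
- n = 210 per arm (300 × 0.70): SE = 0.439, ratio 2.73. Power is 78.0% two-sided and 86.2% one-sided.
- n = 255 per arm (15% missing on average): SE = 0.399, ratio 3.01. Power is 85.3% two-sided.

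The 85% is plausible but cannot be confirmed without the alpha and the simulation parameters. It does not decide this point: it depends on missing data, not on who is labelled a drop-out.

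**2. Exposure of the rule.** 30 − 12 = 18 months, or 18/30 = 60% of follow-up time, lie after the assigned period. Three of the seven follow-up visits (18, 24 and 30 months) fall there.

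**3. One participant, section by section.** Someone uses the app for 12 months, uninstalls at month 13 and attends every visit with a weight.

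| Section | Status |
|---|---|
| 4.4 | Completer |
| 5.4 | Drop-out |
| 7.1 | Still contacted for all follow-ups |
| 7.3 | Not lost to follow-up |
| 9.3 | Analysed |
| 10.1.9.1 | Drop-out (attrition) |

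The same person is a completer and a drop-out. Someone who uninstalls at month 8 and attends every visit may not be a completer under 4.4, but stays in follow-up under 7.1 and is not lost under 7.3, so the conflict with 5.4 remains.

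**4. Effect on reported attrition.** Let u be the share of attenders who uninstall after month 12, and m the share who miss assessments. By the written rule, attrition is at least m + (1 − m) × u; counted by assessments it is m. The documents give no u, so I take 10%, 30% and 50%.
- m = 0: 10%, 30%, 50% by the rule, against 0% of weights missing.
- m = 30% (the planning value for missing data): 0.30 + 0.70 × u = 37%, 51%, 65% by the rule, against 30% missing.

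**5. Effect on the exploratory outcome.** Adherence (6.4) is the percentage of expected activities completed, including self-monitoring. Removing the app ends app-based self-monitoring. If removal also counts as dropout, predictor and outcome share an event and the prediction is partly circular. No expected activity is defined after month 12, yet the outcome can still be triggered then by uninstalling.

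**The case against.** The best defence is that the label does no harm. No primary analysis uses drop-out status, 7.1 and 7.3 govern contact and loss to follow-up, and 9.3 keeps everyone randomized. Section 7.2 also lets the investigator discontinue a participant for significant non-compliance, which could cover early app removal. Most of this stands: the intention-to-treat contrast and the primary hypotheses survive. But 7.2 is discretionary and does not naturally reach someone who has finished the assigned 12 months. The rule is also stated twice without exception, once as the definition of attrition, and dropout is a named exploratory outcome.

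A reader might go further and infer that the 24-month result is really an on-treatment result, or that the plan may not call months 12 to 30 post-treatment. The documents do not support that. They assign 12 months and are silent on later access, which is a gap and not a contradiction. The app is commercially available (1.1), so later voluntary use may itself follow from assignment, and the contrast remains a valid effect of assignment. Section 4.2 claims only short-term durability, with 12-month follow-up.

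Numbers can be attached to the stronger reading, but only by assumption. Suppose a share c of Noom Health participants continues with a 1.2 advantage and the rest keep 0 to 0.4. The difference is then c × 1.2 + (1 − c) × (0 to 0.4). For c = 0.3 this is 0.36 to 0.36 + 0.28 = 0.64; for c = 0.5 it is 0.60 to 0.60 + 0.20 = 0.80. No section gives c or the off-app effect. Section 9.2 plans 1.2 as the difference between whole arms, not among continuing users, and the formula ignores continued use of the limited app by controls. It illustrates a possibility and does not estimate one.

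**Conclusion.** The contradiction is established from the text alone: 5.4 and 10.1.9.1 conflict with 4.4, 7.1 and 7.3 on the status of a participant who removes the app but attends visits. Applied as written, the rule would miscount attrition and contaminate the exploratory dropout outcome. Its size depends on an uninstall rate that the documents do not give. With full attendance, each 10% of participants who uninstall after month 12 adds 10 percentage points (60 of 600) to reported drop-out and nothing to missing weights.

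It does not invalidate the intention-to-treat analysis, the 6- and 12-month hypotheses or the 24-month power statement. On durability the conclusion is limited: the plan has not established that visits after month 12 are off-app, so it should not describe those contrasts as off-app durability without evidence on use.

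**What to change.** 1. Reconcile 5.4 and 10.1.9.1 with 4.4, 7.1 and 7.3. For attrition reporting and the exploratory dropout outcome, count withdrawal from the study or missed assessments, as 7.3 already does. Record app removal, with its date, as intervention status.
2. Reconcile 6.1.2, 1.3 and 9.2 on app access after month 12. What the access rule should be is for the sponsor to state.
3. Sections 10.1.4 and 10.1.9.1 send phone data to the Noom database but give no period, so confirm whether logs exist for months 12 to 30. Where they do, report app use by arm before the 18-, 24- and 30-month visits.
4. Describe those later contrasts as effects of assignment after the assigned period, not as off-app durability, unless continued use is shown to be negligible.

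The cost is wording in the sections named, a small data export if the logs are held, and a slightly narrower durability statement. The primary model and the visit schedule do not change.

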## 6.2 FIDELITY

### 6.2.1 INTERVENTIONIST TRAINING AND TRACKING

Noom Coaches will be trained to monitor the safety of their participants. Additionally, in the introductory material given to all participants, information about how to identify and report a crisis will be outlined. This is to safeguard participants in the event there is a problem with the facilitator. Since this is a non-clinical population (obese individuals without serious psychopathology) and Noom has never had any incidents with their typical overweight population, we do not anticipate this will be a problem. In the event a Coach discovers one of their group members has a serious psychiatric condition (e.g., severe eating disorder, substance dependence), he/she will be instructed to alert Noom and Mt. Sinai immediately via a shared e-mail address (e.g., [contact]). These incidents will be dealt with on a case-by-case basis and the absolute minimal course of action will be to contact the identified participant with relevant psychoeducational material and/or information about where they can go to receive help.

## 6.3 MEASURES TO MINIMIZE BIAS: RANDOMIZATION AND BLINDING

As indicated in the approved Ideate protocol, we will use a randomized-controlled design. Participants will not be blinded to condition.

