**Description of****Sites/Facilities Enrolling****Participants:**

The team at the Icahn School of Medicine at Mount Sinai (ISMMS) is responsible for recruitment, consenting, consulting on the coaching intervention, and data collection and analysis. Research procedures are expected to occur remotely with ISMMS staff.

[figure not shown]

Description of Study	Participants will use the Noom app for 6 months of intervention and 6
Intervention/Experimental	months of maintenance (12 months total).
Manipulation:	
Study Duration:	3-5 years
Participant Duration:	30-32 months

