### 2.3.3 ASSESSMENT OF POTENTIAL RISKS AND BENEFITS

Participants may feel some anxiety related to the lifestyle changes that the intervention asks of them. Noom coaches are trained in managing these difficult situations as part of a standardized Noom Coach Academy lead by licensed clinical psychologist ([name]) who maintains the academy training and regulation. Participants are free to end their participation at any point in the study.

Participants will be told that they are free to not respond or to terminate involvement with the assessment at any time, with no adverse consequences. If a participant appears to be distressed during assessments, research staff will halt the interview and offer to proceed at another time. The interview will only recommence when and if the participant reports feeling capable of doing so. The interviews during the course of the study involve no specific risk or discomfort beyond those of a standard clinical interview. Interviews will be conducted by experienced and well-trained staff sensitive to these issues.

There is a slight risk that research records (questionnaires, consents) might be obtained by persons not authorized to do so. There is a slight risk that research data files might be compromised, and obtained or viewed by unauthorized persons. As described in the data storage section, we have secure databases that will store de-identified data. Only trained research personnel will have access to these files. Noom will have access to subjects' PHI including name, contact info, and demographics. However, Mount Sinai IT security has assessed the risk of potential PHI loss through previous similar work with Noom (IRB-16-01047).

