#### 10.1.6 SAFETY OVERSIGHT

As indicated in the previously approved protocol, [name] will serve as the Principal Monitor. Study data will be reviewed by the investigative team on a monthly basis. Reporting or resolution of any discovered issues will be the responsibility of the study PI. A description of the Data Monitoring Committee has been submitted along with the protocol.

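### Section 6.3 describes no masking of weight observers, outreach staff or analysts, although one team advises on the coaching, collects the data and builds a data-dependent primary model

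*Combined protocol and SAP*

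**What the plan says.** Section 6.3 has two sentences: "As indicated in the approved Ideate protocol, we will use a randomized-controlled design", and "Participants will not be blinded to condition". Staff are not mentioned.

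The roles are set out elsewhere in the combined protocol and SAP:

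- **Team.** The synopsis (1.1, sites and facilities) says the academic team "is responsible for recruitment, consenting, consulting on the coaching intervention, and data collection and analysis", and adds: "Research procedures are expected to occur remotely with ISMMS staff".
- **Weight.** Section 10.1.9.1 has participants weigh themselves by video "with a member of the research team viewing the scale".
- **Interviews.** Section 2.3.3 says: "Interviews will be conducted by experienced and well-trained staff sensitive to these issues". In the list of source records in 10.1.9.1, only the 24-hour dietary recall is called an interview.
- **Missed visits.** Section 7.3 provides for contact throughout the window by telephone, e-mail and a family or friend contact. It does not name the caller.
- **Arm-specific forms.** Section 4.1 sends a 7-point satisfaction scale each month to Noom Health participants and a single question to the control arm.
- **Primary model.** Section 9.4.2 starts from simple linear models and adds complexity according to fit, outliers and possible subgroups. Missing data are first assumed missing at random.
- **Independent check.** Section 10.1.8 plans no independent audits.

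**The concern.** In a trial of two versions of an app, participants cannot readily be blinded. That makes it more important to protect the steps that can be masked: the observed weight, the effort to recover missed visits, and the analysis. The section meant to cover bias leaves all three unaddressed.

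Three things could be affected. First, a weight seen on video is still subject to decisions about whether it counts or should be repeated, and the plan states no rule for these. Section 5.5 records that participants have met such situations: no scale at home, use of a gym scale, a midday call away from the scale. Second, if outreach differs by arm, the weights recovered may differ in kind between arms. Third, a primary model chosen after seeing outliers and possible subgroups, by an analyst who can see the arm, could be steered towards one result without anyone intending it.

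**Working it through.** **1. Is masking of staff described anywhere?** Set against section 6.3, the sections on weights (10.1.9.1), interviews (2.3.3), follow-up (7.1, 7.3), monthly review (10.1.6, 10.1.8) and analysis (9.3, 9.4) contain no statement that anyone is kept unaware of arm.

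**2. Can staff learn the arm?** The plan does not say that they know it, but it creates routes. The monthly forms differ by arm (4.1). Global adherence counts contact with scheduled coach check-ins (6.4), and access to coaches is listed only among the Noom Health features (4.1). Nothing limits who sees this information.

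**3. Which outcomes could masking protect?** The primary objective in section 3 covers weight, quality of life, psychosocial functioning and self-reported health status. Of these only weight is observed by staff. The questionnaires are self-reports by unblinded participants, so masking staff does nothing for that source of bias. The dietary recall could be affected by probing but is not a primary outcome. Retention and model choice affect every outcome.

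**4. Does unequal outreach bias the result?** Not by itself. With arm in a likelihood-based growth model, different retention by arm is harmless if data are missing at random. Bias arises if the participants recovered differ, between arms, in ways related to the unseen weights. The sensitivity analyses named in 9.3 do not go beyond missing at random, so they would not test for this.

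**5. How large a bias would matter?** The plan has no figure to reproduce, so the bias here is an assumption shown over a range. Inputs:

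- SD of BMI change 4.5 (section 9.2);
- 300 per arm (section 4.1), or 600 × 0.70 / 2 = 210 per arm with 30% missing (section 9.2);
- two-sided alpha 0.05, assumed because the plan states none;
- no true effect, and a simple two-arm normal comparison.

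SE = 4.5 × √(2/n), which is 0.367 for n = 300 and 0.439 for n = 210.

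False-positive rate = Φ(b/SE − 1.96) + Φ(−b/SE − 1.96), where b is the shift between arms.

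| Assumed shift b (BMI units) | Share of planned 0.8 | Share of planned 1.2 | Rate, 300 per arm | Rate, 210 per arm |
|---|---|---|---|---|
| 0.1 | 12.5% | 8% | 5.9% | 5.6% |
| 0.2 | 25% | 17% | 8.5% | 7.4% |
| 0.3 | 37.5% | 25% | 12.9% | 10.5% |

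The planned analysis is a piecewise growth model, so its standard error will differ. The table shows only that a shift well below the planned differences would matter if it occurred. It is not evidence that one will.

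**The case against.** The strongest reply is that silence is not a finding. Section 6.3 refers to an approved Ideate protocol and section 10.1.10 to a manual of procedures. Neither is in the documents, and either might describe masking. A reader might infer that no one is masked; the documents say this only of participants.

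Other stronger readings also fail:

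- **The same people do everything.** The overlap is shown for the team only. Noom's own coaches deliver the coaching (2.3.3, 4.1, 6.2.1) and the academic team consults on it, so delivery and assessment are already partly separated.
- **Staff decide how hard to pursue each participant, or which weights to keep.** No section grants that latitude. Sections 7.1 and 7.3 set one contact rule for all. The gap is that there is no fixed number of attempts and no rule on accepting readings. Video observation itself limits misreporting.
- **The monthly review is an unmasked look at the treatment effect.** Section 10.1.8 describes an audit of individual cases for missing data and entry errors, and 9.4.6 plans no interim analysis.
- **The bias has a known size or is beyond any analysis.** The documents support no figure for a weight shift or a retention gap, and nothing in them shows that analysis could not address it.

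Finally, the footnote to section 5.2 shows that recruitment has closed, so some staff may already know arms. Some need to: research staff judge relatedness of events (8.3.3.2), and section 7.2 has the study stop the intervention in certain cases.

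All of this narrows the point. It leaves standing that no masking of weight observers, outreach staff or analysts is described, and that the primary model depends on the data.

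**Conclusion.** The concern holds in limited form. As written, the plan leaves weigh-ins, outreach and the choice of primary model open to knowledge of arm, within a team that also advises on the experimental coaching. Model choice is the clearest exposure, because section 9.4.2 itself provides for data-dependent changes. Observer bias in a scale reading viewed on video has less room.

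The size of any bias is unknown. The illustration rests on an assumed shift, an assumed alpha and a simplified comparison. The conclusion also assumes that the documents not available here do not already describe masking. If they do, stating it in section 6.3 settles the point. Better masking would reduce the risk for weight, retention and analysis. It would not touch bias in the questionnaires completed by unblinded participants.

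**What to change.** For the steps still to come, add a paragraph to section 6.3 that states:

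1. **Masked contact staff.** The arm field and the arm-specific forms in REDCap are hidden from staff who run weigh-ins, dietary recalls and outreach. Participants are asked at the start of each call not to mention their app version, and any unmasking is recorded.
2. **Same procedure in both arms.** One scripted contact schedule and one written rule for accepting or repeating a weight apply regardless of arm.
3. **Model fixed first.** The analyst settles the primary model, outlier handling and growth form on coded or pooled arms before arm labels are released. Coach check-in data should be withheld until then, since they would reveal the code.
4. **Exemptions.** Staff who must know the arm, for example to judge relatedness of events or to stop the app, are exempt and listed by role.

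The cost is a change of REDCap user rights, a call script and the paragraph itself. Items 1 to 3 need no new participants or measurements. The downside is small: some participants will reveal their arm and some staff may already know it, so masking will be incomplete and should be reported as such.
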